7.5.3.2 Tumor Tissue for Biomarkers

Available tumor tissue will be collected to investigate potential predictive markers of clinical response. Any sample since initial diagnosis is acceptable, but if several samples are available, the most recent sample is preferred. Tumor tissue (FFPE block preferred) should be submitted once it has been determined that the patient meets all other eligibility criteria and is scheduled to proceed with study drug administration.

Please refer to the laboratory manual for detailed instructions regarding specimen handling and shipment.

^{*} Postdose timepoint is counted from start of infusion.

7.6 Health-Related Quality of Life (HRQoL) Questionnaires

7.6.1 EuroQoL-5 Dimensions-5 Levels (EQ-5D-5L)

The EQ-5D-5L is designed as an international, standardized, generic instrument for describing and evaluating QoL (EuroQoL Group, 1990). This questionnaire can be completed by patients ≥12 years of age. The EQ-5D-5L consists of 2 parts:

- The descriptive system: QoL is classified according to 5 dimensions: mobility, self-care, usual activities, pain/discomfort, and anxiety/depression. Each dimension comprises 5 levels of perceived problems (e.g., none, slight, moderate, severe, extreme).
- The visual analog scale (VAS): patients are asked to indicate their health state today on a VAS with the endpoints labeled 'the best health you can imagine' (score 100) and 'the worst health you can imagine' (score 0). Patients are asked to mark an "X" on the VAS to indicate their own health and then to report the score in a text box. If there is a discrepancy between where the patient has placed the X and the number he/she has written in the box, the number in the box is to be entered in the CRF together with a comment indicating the discrepancy.

8.1.1 Adverse Events of Special Interest

For this study the following adverse events, irrespective of seriousness and causality, are considered AESIs:

- GBS (including variants such as acute motor and sensory axonal neuropathy)
- Polyradiculopathy
- Autonomic nervous system imbalance
- Nerve palsy
- \(\geq \) Grade 3 neurologic toxicities

- \(\geq\)Grade 3 immune-mediated toxicities. Of note, rashes will not be considered as immune-mediated skin toxicities, since they are well described toxicities of PBD-dimers; with exception for Stevens-Johnson syndrome, toxic epidermal necrolysis, acute generalized exanthematous pustulosis, exfoliative dermatitis, and drug reaction with eosinophilia and systemic symptoms.
- Autoimmune-mediated events (such as, but not limited to, pneumonitis, hepatitis, colitis, endocrinopathies, type 1 diabetes mellitus, and nephritis/renal dysfunction)

For all AESIs it is important to provide as much information as possible: e.g., time of onset (including changes in severity), duration of events, time to resolution, and relationship to camidanlumab tesirine. It is also important to specify if any AEs are autoimmune mediated.

AESIs will be closely monitored and followed.

8.2 Eliciting and Reporting Adverse Events/Adverse Events of Special Interest/Serious Adverse Events

Patients will be instructed to contact the Investigator at any time after ICF signature if any symptoms develop. At each study visit, patients will be asked a non-leading question to elicit any medically related changes in their well-being. Patients may also report AEs voluntarily and they will be instructed to contact the Investigator between visits if any symptoms develop or worsen.

All AEs will be reported starting when the patient provides written informed consent. Clinically significant medical conditions present at the time of ICF signature will be reported as medical history. Clinically significant medical conditions that start or worsen after ICF signature will be reported as AEs.

All AEs, AESIs, and SAEs, regardless of relationship to study drug, will be reported from the time the patient signs the ICF until 30 days after the last dose of study drug; thereafter, only related SAEs will be reported [For German Sites Only: thereafter, only SAEs will be recorded (irrespective of the relationship to the study drug)]. The exception to this is patients who have responded to camidanlumab tesirine and undergo HSCT (either autologous or allogeneic) after permanent discontinuation of camidanlumab tesirine treatment without any intervening anticancer therapy to treat relapsing disease (mobilization/conditioning treatment for HSCT is allowed) or who have received CAR-T as the immediate subsequent anticancer therapy (mobilization/conditioning treatment for CAR-T is allowed). These patients will have the following safety information reported until 180 days post-HSCT/post-CAR-T regardless of relationship to camidanlumab tesirine:

- \geqrapsize Grade 3 AEs suggestive of hepatic toxicity, veno-occlusive disease/sinusoidal obstruction syndrome, graft-versus-host disease, infectious complications, potentially immune-mediated adverse events, prolonged cytopenia(s), and pulmonary toxicity
- In addition, for CAR-T therapy, any ≥ Grade 3 AEs of cytokine-release-syndrome and neurological toxicity

- SAEs
- Death

Whenever possible, AEs should be reported as a diagnosis rather than individual signs and symptoms. If no diagnosis is available or has been identified, then the primary symptom is reported.

In general, the term 'disease progression' should not be used for reporting an AE/SAE. However, AEs/SAEs that are complications of disease progression should be reported.

All AEs reported or observed during the study will be recorded on the AE page of the eCRF. Information to be collected will include event term, date of onset, assessment of severity (Section 8.3), seriousness (Section 8.1), relationship to study drug (Section 8.4), action taken with study drug, date of resolution of the event or ongoing (when no resolution by the end of the reporting period), any required treatment or evaluations, and outcome.

New serious AESIs/SAEs and any recurrent episodes, progression, or complications of the original AESI/SAE must be reported to the pharmacovigilance department of the Sponsor or delegate (e.g., contract research organization [CRO]) within 24 hours after the time site personnel first learn about the event. Reporting will occur through the electronic data capture (EDC) system.

Any recurrence of GBS/polyradiculopathy, irrespective of the relationship to study drug, has to be reported to the Sponsor, including when the recurrence occurs when the patient has already completed the study. The reporting of such events after the patient has completed the study will be captured via the Sponsor's safety database and therefore will not impact database lock.

Non-serious AESIs must be entered in the EDC system and reported to the Sponsor or delegate (e.g., CRO) within 48 hours after the time site personnel first learn about the event.

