Pregnancy test, if applicable	7.4.6	X	On C1D1,		on D1 of every 6 wks apart)	other cycle (max.	X^6	

	Protocol Section	Screening	Treatment Period			Follow-up Period (up to 3 years from EOT)		
(1 Cycle = 21 days)			Cycle 1 and	Cycle 1 and Cycle 2 (C1 and C2) C3 a			EOT	Every 12 weeks (wks)
Day (D)		-28 to −1	1	8	15	1		
12-lead ECG	7.4.7 Table 3	X	X (Pre, EOI, Post)	X	X	C3 and C4 (Pre, EOI), C5 then every other cycle (Pre)	X	
Premedication	6.7.1		D-1 to D2			D-1 to D2		
Camidanlumab tesirine administration	6.3		X			X		
PK sample	7.5.1 Table 4		X (Pre, EOI, Post)	X	X	C3 through C6 (Pre, EOI), then every cycle (Pre)	X	
ADA sample	7.5.2 Table 4		X (Pre)		X C1 only	C3 (Pre), then every other cycle (Pre)	X^7	
Soluble biomarkers	7.5.3.1 Table 5		X (Pre, Post)	X	X	C3 (Pre, EOI), then every other cycle (Pre)	X	
cfDNA samples (gDNA only at C1D1 and EOT)	7.5.3.1		X (Pre)			6 and 12 weeks postdose (with disease assessment)	X	X at disease progression
HRQoL ⁸	7.6		X			X	X	
Concomitant medications ⁹	6.8	Fro	From ICF signature date or D-14, whichever is earlier, until 30 days after last dose of study drug					
Adverse events	8	AE/SAE	AE/SAEs from ICF signature date until 30 days after last dose of study drug; thereafter, related SAEs only					
1 st New anticancer treatment	4.2.3						X	X
Survival	4.2.5						X	X

Abbreviations: ADA, anti-drug antibody; AE, adverse event; BP, blood pressure; cfDNA: circulating cell-free DNA; ECG, electrocardiogram; ECOG, Eastern Cooperative Oncology Group; EOI, end of infusion; EOT, end of treatment; HR, heart rate; gDNA, genomic DNA; HRQoL, health-related quality of life; ICF, informed consent form; PK, pharmacokinetics; post, postdose; pre, predose; RR, respiratory rate; SARS-CoV-2: respiratory syndrome coronavirus 2; SAE, serious adverse event; Temp, temperature; VZV, varicella zoster virus.

- Screening imaging must be performed within 4 weeks prior to C1D1 and the same assessment method should be used throughout the study. Week 6 imaging should be performed within 1 week prior to C3D1 and Week 12 imaging should be performed within 1 week prior to C5D1. All other imaging for disease assessment for patients on study drug should be performed within ±2 weeks of the scheduled timepoint. Disease assessments should be performed at the timepoints specified even if study drug dosing is delayed. If a scan has been performed within 6 weeks of EOT, it does not need to be repeated at EOT.

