4.8.1 Adverse Events, Serious Adverse Events, and Deaths

4.8.1.1 Analyses of adverse events

The primary focus of adverse event reporting will be on TEAEs. An adverse event (AE) will be considered to be a TEAE if it begins or worsens on or after the first dose date and until 30 days after the last dose date, or start of a new anticancer therapy/procedure, whichever comes earlier.

An AE occurring before the first dose or more than 30 days after the last dose date or after the start of a new anticancer therapy/procedure will not be included in TEAE displays, but will be listed as non-TEAEs.

If an AE date/time of onset (occurrence, worsening, or becoming serious) is incomplete, an imputation algorithm will be used to classify the AE as pre-treatment, TEAE, or post-treatment. The algorithm for imputing date/time of onset will be conservative and will classify an AE as treatment-emergent unless there is definitive information to determine it is a non-TEAE (pre- or post-treatment). Some details on classification of AEs with missing or partial onset dates are provided in Section 8.

Analysis of all TEAE(s):

The following TEAE summaries will be generated for the all-treatment population.

- Overview of TEAEs, summarizing number of TEAE and number (%) of patients with any
 - TEAE
 - Related TEAE (including possibly related, probably related, or related)
 - Any TEAE \geq Grade 3
 - Serious TEAE
 - TEAE leading to death
 - TEAE leading to permanent treatment withdrawal
 - TEAE leading to camidanlumab tesirine delay or reduction or interruption (if applicable)
 - TEAE with at least one infusion related reaction
 - TEAE of special interest
- All TEAEs \geq Grade 3 by PT, showing number (%) of patients with at least one TEAE, sorted by decreasing incidence of PTs
- All post-treatment/treatment-emergent AEs of special interest by PT, showing number (%) of patients with at least one TEAE of special interest, sorted by decreasing incidence of PTs
- All TEAEs by primary System Organ Class (SOC) and PT, showing number (%) of patients with at least one TEAE, sorted by SOC in alphabetic agreed order and decreasing incidence of PTs within SOC. This sorting order will be applied to all other tables, unless otherwise specified.

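### Three SAP displays pool treatment-emergent with selectively collected post-treatment events, and one of them labels the pooled AESI count as TEAEs

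*Protocol*

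**What the plan says.** **Definition.** Protocol 8.1.1 sets the scope of AESIs without regard to seriousness or cause: "For this study the following adverse events, irrespective of seriousness and causality, are considered AESIs".

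**Collection.** Protocol 8.2 names AESIs, alongside AEs and SAEs, in a window that runs from consent "until 30 days after the last dose of study drug; thereafter, only related SAEs will be reported". Table 1 repeats the limit: "AE/SAEs from ICF signature date until 30 days after last dose of study drug; thereafter, related SAEs only". Protocol 8.2 gives these exceptions after day 30:
- German sites record all SAEs, whatever the causality.
- Responders who go on to HSCT, and patients whose immediate next therapy is CAR-T, have SAEs, deaths and listed Grade 3 or higher events reported to day 180 after the procedure.
- Recurrence, progression or complications of an original AESI or SAE are reportable.
- Recurrence of GBS/polyradiculopathy is reportable at any time, even after the patient has completed the study.

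Two sentences in the same section carry no end date: "All AEs reported or observed during the study will be recorded on the AE page of the eCRF" and "Non-serious AESIs must be entered in the EDC system and reported to the Sponsor or delegate (e.g., CRO) within 48 hours".

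**Analysis.** SAP 4.8.1.1 closes the TEAE window at 30 days after the last dose or at the start of new anticancer therapy, whichever is earlier. It says that an event more than 30 days after the last dose or "after the start of a new anticancer therapy/procedure will not be included in TEAE displays, but will be listed as non-TEAEs". It then specifies "All post-treatment/treatment-emergent AEs of special interest by PT, showing number (%) of patients with at least one TEAE of special interest". Two further displays in the section also take post-treatment and treatment-emergent events together: AESIs by SOC, PT and maximal grade, and events grouped by SMQ, modified SMQ or pre-specified SOC.

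**The concern.** An AESI table is normally read as the share of patients who had the event over a defined period in which everyone was observed alike. These three displays combine periods with different capture rules. Up to day 30 every event is collected. After day 30, whether an event reaches the table depends on its seriousness, the investigator's causality judgement, the country of the site, and whether the patient went on to HSCT or CAR-T. Two patients with the same late event can be counted differently.

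The by-PT display has a second problem. Its title admits post-treatment events, but its count is of TEAEs. A programmer cannot satisfy both, and a reader of the clinical study report could not tell which was followed.

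The safety interpretation is at stake. Protocol 1.3 classes neurologic and immune-related events, including polyradiculopathy and GBS, as important identified risks, and these are the events the AESI displays are meant to describe.

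**Working it through.** The plan gives no figure to reproduce, so the check sets the collection rule beside the display rule.

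**Step 1. Classify AESIs by onset.** The protocol's collection window does not close when new anticancer therapy starts, but the SAP's TEAE window does. That gives three classes:

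| Onset | Captured (Protocol 8.2, Table 1) | SAP status | In the pooled displays? |
|---|---|---|---|
| First dose to day 30 after last dose, before any new therapy | All | TEAE | Yes |
| Within 30 days of last dose, after new therapy | All | Not TEAE | Yes |
| Beyond day 30 after last dose | Related SAEs plus the exceptions | Not TEAE | Yes, if collected |

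The first two rows are completely collected and the third is selected. The displays add all three.

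**Step 2. Check the label.** For incomplete onset dates, SAP 4.8.1.1 sorts each event as pre-treatment, TEAE or post-treatment, so the last two are separate classes. A display that includes post-treatment events cannot also be a count of patients with a TEAE. The label conflict appears only in the by-PT display; the pooling appears in all three. The overview row for TEAEs of special interest stays purely treatment-emergent.

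**Step 3. Identify what is missing after day 30.** An AESI falls outside collection if it is a first onset and is either non-serious or, outside Germany, serious but judged unrelated, unless the HSCT/CAR-T rule applies.

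**Step 4. Size.** The undercount cannot be computed, because it needs a late-onset rate and a capture share, and the documents give neither. An illustration on assumed numbers shows only the form of the problem. Take 100 patients, 20 with a treatment-emergent AESI, and 5 or 10 others with a true late first onset, of which 25% to 75% are captured:
- 5 late cases: 20 + 5 × 0.25 = 21.25 to 20 + 5 × 0.75 = 23.75, against 25 with full capture.
- 10 late cases: 20 + 10 × 0.25 = 22.5 to 20 + 10 × 0.75 = 27.5, against 30 with full capture.

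With 100 patients these counts are also percentages. In each case the pooled figure matches neither the treatment-emergent incidence (20%) nor the complete one (25% or 30%).

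**The case against.** The strongest reply is that the 30-day limit is deliberate. Protocol 8.2 states it, Table 1 repeats it, and the TEAE window uses the same 30 days. The AESI definition in Protocol 8.1.1 says which events qualify and promises no longer collection period. This stands, so the limit is a design choice and not an error.

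A reader might infer that serious late toxicity is largely lost. The documents do not support that:
- The SAE definition in Protocol 8.1 includes important medical events, so many severe AESIs would qualify.
- Protocol 8.4 calls an event related if there is a reasonable possibility of a causal link. Eligibility requires a prior checkpoint inhibitor, which gives a late autoimmune event a rival explanation, but that alone does not make the event unrelated under this test.
- Most late GBS would probably still arrive as a related SAE.

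A reader might also see a contradiction in the undated sentences on recording AEs and on the 48-hour deadline. They read most naturally as working inside the stated window. The result is an ambiguity that sites could resolve differently.

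A third inference is that collection should be extended. Protocol 7.4.6 equates 9.5 months with five half-lives plus 6 months, which implies 9.5 − 6 = 3.5 months, or 3.5 × 30.44 = 106.5 days (day 107). That figure concerns exposure for contraception and is not evidence on when AESIs occur. Protocol 1.3 describes the study as ongoing, so a uniform new window would need an amendment and retrospective collection, or would leave two cohorts. It is a trade-off for the sponsor and not a correction this point can require.

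Finally, collected late events are listed separately, the overview row is clean, and safety analyses are descriptive. All true, but the summary tables would still carry the mixed percentage.

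**Conclusion.** The concern holds for the SAP displays. If followed as written, SAP 4.8.1.1 yields percentages that mix completely and selectively collected events in three displays, and in the by-PT table puts them under a TEAE label that conflicts with the section's own rule.

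The late component can only be too low, by an amount the documents do not allow anyone to estimate. The events not collected are probably mainly lower-grade, non-serious first onsets, with some serious ones judged unrelated. The primary ORR analysis is untouched.

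The conclusion rests on reading the day-30 limit as governing AESIs, which both Protocol 8.2 and Table 1 support. There is one caveat. SAP Section 1 says it was developed from protocol amendment 1, while the protocol reviewed here is at Amendment 5. Amendment 1's adverse event wording is not available, so it cannot be said whether the mismatch was there from the start.

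**What to change.** Change SAP 4.8.1.1 only. In the AESI display by PT, the AESI display by SOC, PT and grade, and the grouped SMQ display:

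1. Show treatment-emergent events separately from post-treatment events.
2. Split post-treatment events into onset within 30 days of the last dose but after new anticancer therapy (fully collected), and onset beyond day 30 (selectively collected).
3. In the by-PT display, keep the TEAE label for the treatment-emergent part only.
4. Add a footnote: beyond day 30 only related SAEs are collected, apart from all SAEs at German sites, the selected events to day 180 after HSCT/CAR-T, recurrence or progression of an original AESI or SAE, and recurrence of GBS/polyradiculopathy at any time. State that the beyond-day-30 count is not an incidence.

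The cost is slightly longer table shells and one footnote. No change to the protocol or to data collection is needed.

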8.3 Assessment of Severity

All AEs will be graded according to CTCAE v4.0. For events not included in the CTCAE criteria, the severity of the AE is graded on a scale of 1 to 5 as shown in Table 6.

Table 6 Definition of Severity Grades for CTCAE

Grade	Definition
1	Mild; asymptomatic or mild symptoms; clinical or diagnostic observations only; intervention not indicated.
2	Moderate; minimal, local, or noninvasive intervention indicated; limiting age-appropriate instrumental activities of daily living (ADL). ^a
3	Severe or medically significant but not immediately life threatening; hospitalization or prolongation of hospitalization indicated; disabling; limiting self-care ADL. ^b
4	Life-threatening consequences; urgent intervention indicated.
5	Death related to adverse event.

a. ADL refers to preparing meals, shopping for groceries or clothes, using the telephone, managing money, etc.

The AEs characterized as intermittent do not require documentation of onset and duration of each episode.

8.4 Assessment of Causality

The Investigator's assessment of an AE's relationship to study drug is an important part of safety reporting but is not a factor in determining whether an AE is reported. An AE will be assessed as related to study drug if there is a reasonable possibility of causal relationship with the use of the study drug. For SAEs, whenever possible, the Investigator should provide a rationale for the causality assessment.

8.5 Regulatory Reporting

Reporting of AEs to competent authorities and Independent Ethics Committees (IECs) will be consistent with local laws, regulations, guidelines, and requests.

8.6 Pregnancy Reporting

Any pregnancy in a patient that occurs from signing the ICF up to 9.5 months after the last dose of study drug, whichever occurs last, must be reported using the Pregnancy Report Form. Any pregnancy in a partner of a male patient that occurs from signing the ICF up to 6.5 months after last dose of study drug must be reported. Pregnancy must be reported within 24 hours after the site personnel first learn of the pregnancy. The pregnancy itself is not considered an AE. However, the pregnancy must be followed to determine outcome (including spontaneous miscarriage, elective termination, normal birth, or congenital abnormality) and status of mother and child, even if the patient discontinued from the study. Abortions (elective or spontaneous) must be reported as an SAE.

Any SAE occurring in association with a pregnancy that is brought to the Investigator's attention after the patient has completed the study and considered by the Investigator as possibly related to the study drug must be promptly reported in the same manner.

b. Self-care ADL refers to bathing, dressing and undressing, feeding self, using the toilet, taking medications, and not bedridden.

Once pregnancy is confirmed in a study participant, study drug will be discontinued; see Section 7.4.6 for additional information.

8.7 Independent Data and Safety Monitoring Board

An iDSMB will primarily ensure the safety of patients enrolled in this study by providing expertise and recommendations for further study conduct and progress, which concern the continuation, modification, or termination of the study.

The iDSMB will be composed of at least one clinician with immuno-oncology expertise and a biostatistician. The board will meet periodically to review data, and as soon as possible upon occurrence of polyradiculopathy/GBS and possibly other relevant \geq Grade 3 autoimmune or neurologic toxicities (see Section 4.3) or other concerning safety issues.

Details regarding the iDSMB responsibilities, authorities, and procedures will be included in a separate iDSMB charter.

9 Statistical Considerations

Full details of the analysis plan, including a more technical and detailed elaboration of the statistical analyses, will be provided in the statistical analysis plan (SAP). Results for the exploratory/correlative analyses may be reported separately.

